
Randomization procedure. [name] (Co-I) will generate a randomization list using a computer software and seal the list in opaque envelopes. The on-site research coordinator will open one envelope after a patient has completed the baseline assessments. If the patient is assigned to the ADL-enhanced group, the coordinator will notify the study OT to start intervention.

Study Intervention.

Description of ADL-enhanced intervention. The experimental arm will receive the enhanced-ADL program in 6 home visits from a study OT in addition to usual rehabilitation therapy. The 6 study visits will be delivered over

a 6-week period. The study OT visits will occur separately from usual therapy visits. If the patient cancels a study OT visit, the visit will be rescheduled. The patient will have a 21-day window to resume the intervention. The study OT will apply the compensatory approach in the first 2 visits and the restorative approach in the other 4 visits. Both approaches respect and incorporate the patient's activity preferences in the patient-centered treatment plan. The study OT and the patient collaborate to identify and address ADL tasks that are important and meaningful for the patient's independence.

Compensatory approach procedures. The study OT will conduct a semi-structured interview in the 1st visit to understand the patient's daily routine and to identify two or three ADL tasks that are meaningful but difficult for the patient because of reduced intrinsic capacity. The study OT and the patient collaboratively decide which energy conservation techniques to apply. The patient practices applying these techniques to the selected ADL tasks. The patient is instructed to carry out these ADL tasks with practiced energy conservation techniques until the next visit.

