Restorative approach procedures. The study OT will deliver the restorative approach starting at the 3rd visit. The selected self-care tasks include any in-home activities that the patient does to take care of self and others, which are not limited to basic ADL. In the beginning of each visit, the study OT and the patient together identify 2 or 3 activities where the patient has experienced limitations or difficulties. The study OT will apply one or two activity grading principles to each selected activity. The intervention intensity will be kept at the moderate level (somewhat hard) using the Omni Scale, which is a rated perceived exertion scale. For example, if a patient experiences difficulty to returning pantry items to overhead shelves, the study OT can let the patient wear a weighted wrist cuff while sorting pantry items (increase the load), restore items to an overhead versus shoulder-high shelf (increase the movement distance), restore items into different locations on the shelves (change of movement direction), speed up while storing items (increase the movement speed), store 10 pantry items versus store five items at a time (increase the endurance), or carry groceries with a shopping bag and store pantry items from the groceries to the overhead shelves (increase the activity complexity by combining two tasks, carrying groceries and sorting the pantry items after shopping). Patients will practice each selected task for 15 to 20 minutes with a rest break if needed.

Allowed interventions. All participants will receive the care plan approved by their home health agency. The care plan should include regular home health rehabilitation therapy.

Adherence Assessment. The adherence for the ADL-enhance intervention will be evaluated by the number of sessions that the patient is able to complete within the study period (60 days).

Study Procedures.

[figure not shown]
6.1. Schedule of Evaluations.

	Baseline	Post-intervention (Post intervention \pm 7 Business days) ⁺	One-month follow-up (Day 30 post intervention \pm 7 Business days)	3-month follow-up (Day 90 post intervention \pm 7 Business days)
Assessment of Motor and Process Skills	x	x	x	
Activity Measure for Post-Acute Care Home Health Short Form	x	x	x	x
OASIS self-care items from chart review	x	x		
Box and Block Test	x	x	x	
Jebesen Hand Function Test	x	x	x	
Timed-Up-and-Go Test	x	x	x	
Short Physical Performance Battery	x	x	x	
PEG three-item scale	x			
Patient Health Questionnaire-9	x			

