Saint Louis University Mental Status Exam	x			

Patient demographic background and medical info from self-report as well as chart review	x			
Patient satisfaction survey		x		
Adverse events (hospitalization, falls, emergency room visits)		x	x	x

+: The end of ADL-enhanced program, the last home visit of usual care, or 6 weeks from the baseline assessment, which occurs last.

Study visit schedule.

Description of Evaluations.

Screening evaluation.

The screening will occur over the phone within three business days after a home health care provider has mentioned the study opportunity to the patient and received verbal permission from the patient for the research coordinator to contact him/her. The research coordinator will follow a phone script approved by the UF IRB for this phone screening. The coordinator will obtain a verbal permission prior to proceeding with screening questions from the potential research participant after a brief introduction of the study. These screening questions are:

1. Are you aged 65 years or above?
2. How many medical conditions, including chronic conditions, that you currently have? Examples of the conditions include but not limit to diabetes, heart disease, high blood pressure, joint disease or arthritis, and lung disease.
3. Do you have any of the following conditions?
 - an elective joint replacement surgery in the last month
 - orthopedic or heart surgery in the last month
 - lower extremity amputation
 - currently receiving treatment for cancer
 - an ongoing dialysis treatment
 - a neurologic condition, such as stroke or Parkinson's disease, that significantly limits your movements
 - congestive heart failure that is at the terminal stage

In addition to these questions, the interviewer will administer the "Six-item cognitive screener" to determine the potential participant's cognitive ability. If a participant scores a 4, 5, or 6 on the screener, they will be eligible for the study.

Enrollment, baseline, and randomization.

Enrollment. A patient is considered enrolled in this study when he or she meets the eligibility criteria and signs the informed consent form.

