Randomization. Randomization will occur after the baseline assessment. [name] (Co-I) will generate a randomization list using a computer software and seal the list in opaque envelopes. The on-site research coordinator will open one envelope after a patient has completed the baseline assessments. If the patient is assigned to the ADL-enhanced group, the coordinator will notify the study OT to start intervention.

Post-intervention evaluation.

The satisfaction survey will be given to the patient in the experimental group after the last visit of ADL-enhanced intervention by the research coordinator over the phone.

For the group that will receive the ADL-enhanced program, the post-intervention evaluation conducted by the blinded outcome assessor will occur within seven business days after the completion of the last visit of usual home health rehabilitation therapy or ADL-enhanced intervention, whichever occurs last. For the control group, the post-intervention evaluation conducted by the blinded outcome assessor will occur either 6 weeks after the baseline assessment or after the last usual home health visit, whichever occurs last. Patients will be instructed not to discuss their therapy content with the blinded outcome assessor and vice versa. The following assessments will be administered during the post-intervention evaluation visit.

1. Assessment of Motor and Process Skills
2. Activity Measure of Post-Acute Care Home Health Short Form
3. Jebsen Hand Function Test
4. Box and Block Test
5. Timed-Up-and Go
6. Short Physical Performance Battery
7. Adverse events questionnaire

The research coordinator will extract the patient's OASIS self-care item scores (scores at the start of care and discharge) from medical chart when the patient has been discharged from home health care or 60 days after admission.

One-month follow-up evaluation.

The one-month follow-up evaluation conducted by the blinded outcome assessor will occur within seven business days one month after the completion of the last visit of usual home health rehabilitation therapy or ADL-enhanced intervention (Day 30 post intervention), whichever occurs the last. Patients will be instructed not to discuss their therapy content with the blinded outcome assessor and vice versa. The following assessments will be administered during the one-month follow-up evaluation visit.

1. Assessment of Motor and Process Skills
2. Activity Measure of Post-Acute Care Home Health Short Form

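### The primary-outcome visit has conflicting anchors: the visit text omits the 6-week minimum for the experimental arm only, and no date is set for patients who stop the programme

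*Combined protocol and SAP*

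**What the plan says.** The document describes the timing of the post-intervention visit in three places.

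- **Post-intervention evaluation, experimental arm.** The visit is due "within seven business days after the completion of the last visit of usual home health rehabilitation therapy or ADL-enhanced intervention", counted from the later of the two. No minimum time from baseline is given.
- **Post-intervention evaluation, control arm.** The visit takes place "either 6 weeks after the baseline assessment or after the last usual home health visit, whichever occurs last".
- **Schedule of Evaluations (6.1).** The footnote anchors the same visit at "The end of ADL-enhanced program, the last home visit of usual care, or 6 weeks from the baseline assessment, which occurs last", without separating the arms. The column heading allows 7 business days on either side, whereas the experimental-arm text allows only days after the anchor.

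On cancelled study visits, the description of the ADL-enhanced intervention says "The patient will have a 21-day window to resume the intervention". It does not say when the 21 days start. Nothing says how the last visit, or the end of the programme, is fixed for a patient who does not resume.

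The one-month visit is labelled "Day 30 post intervention" in both the schedule and the text. The text counts it from the last therapy visit and does not mention the 6-week term.

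**The concern.** The Motor Skills score of the Assessment of Motor and Process Skills is the primary outcome, and treatment completion is the first time point of the primary objective. The Activity Measure short form and the four physical-function tests are taken at the same visit.

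If sites follow the visit text, timing depends on arm. A control is not due before 6 weeks, but an experimental patient who stops early after usual care has ended is due within days of the last attended visit. Elapsed time since baseline then differs between arms for reasons tied to stopping. The Data analysis plan fits a quadratic curve over three time points. It does not say whether time is nominal or actual, and it gives no rule for missing or out-of-window visits.

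A second difficulty arises in the experimental arm only. While the resume period is open, the site may not know whether the last attended visit was the final one. It must then either assess a patient who may still resume, or wait and miss the window.

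**Working it through.** There is no stated figure to reproduce, so this is calendar arithmetic. Day 0 is baseline, A is the day of the last attended study visit, and U is the day of the last usual-care visit. Inputs from the document: 7 business days, 21 days, 6 weeks = day 42, Day 30. Assumptions: weekly study visits, first visit on day 7, no public holidays.

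**1. Window length.** Seven business days from a Monday, Tuesday or Wednesday is 9 calendar days. From a Thursday or Friday it is 11. The range is 9 to 11.

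**2. Arms compared under the visit text.** Suppose usual care has ended by day A. The experimental window closes at A + 9 to A + 11. A control with the same usual care is due at day 42.

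| Last attended visit | A | Window closes | Days before day 42 |
|---|---|---|---|
| 1 | 7 | 16–18 | 24–26 |
| 2 | 14 | 23–25 | 17–19 |
| 3 | 21 | 30–32 | 10–12 |
| 4 | 28 | 37–39 | 3–5 |
| 5 | 35 | 44–46 | closes after day 42 |

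**3. Resume period under the visit text, usual care over.**
- 21 days run from the last attended visit: the window closes 21 − 11 = 10 to 21 − 9 = 12 days before the period ends.
- 21 days run from a cancelled visit one week later: 28 − 11 = 17 to 28 − 9 = 19 days before.
- Usual care continuing: the window closes at U + 9 to U + 11. On the first count there is no clash once U is at least 10 to 12 days after A.

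**4. Resume period under the footnote.** The window cannot close before 42 + 9 = 51 to 42 + 11 = 53.
- Counting from the last attended visit, a clash needs A + 21 > 51 to 53, so A > 30 to 32.
- Counting from a cancelled visit one week later, it needs A + 28 > 51 to 53, so A > 23 to 25.

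With usual care over by day 42:

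| Last attended visit | A | Resume period ends (two counts) | Shortfall (days) |
|---|---|---|---|
| 3 | 21 | 42 or 49 | none |
| 4 | 28 | 49 or 56 | none, or 3–5 |
| 5 | 35 | 56 or 63 | 3–5, or 10–12 |

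If usual care runs to day 56, the window closes at day 65 to 67 and none of these cases clash.

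**5. One-month visit.** Counted from the last therapy visit, its window opens at 30 − 11 = 19 to 30 − 9 = 21 days and closes at 39 to 41. A patient confirmed as stopped at day 21 leaves 39 − 21 = 18 to 41 − 21 = 20 days for both visits.

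The anchors also differ. If all therapy ends on day 14, the footnote dates the post-intervention visit at day 42, while the one-month text gives 14 + 30 = day 44. The control-arm visit text leads to the same 2-day gap for a control whose usual care ends on day 14.

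**The case against.** The strongest reply is that the footnote already supplies the 6-week minimum for both arms. A site that follows it has no early-assessment problem, and most of the clash with the resume period disappears. The footnote also speaks of the end of the programme, not of the last attended visit. For a patient who never resumes, that could be read as the day the 21 days lapse, which would remove the clash altogether. Some patients will simply say that they are stopping, so nobody has to wait. With the schedule's two-sided window, a control could be seen from day 31 to 33 (42 − 11 to 42 − 9), which narrows the gap in step 2.

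Much of this stands, and it confines the problem. It does not remove it. The visit text gives the 6-week term to controls and leaves it out for the experimental arm, so a site following that section has no minimum. The reading of programme end as the lapse of 21 days is possible but not stated. Even against a control seen at day 31 to 33, a patient stopping after visit 1 is assessed at least 31 − 18 = 13 days earlier.

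A reader might infer more than the document supports:

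- **That any stopper loses the primary-outcome window.** The anchor is the later of two visits, so continuing usual care protects the patient, and under the footnote early stoppers are protected too.
- **That the post-intervention and one-month visits must merge.** Step 5 shows room for both. The first would be late.
- **That up to 5 of 24 experimental patients are affected.** A completion rate above 75% needs at least 19 of 24 (79%), leaving 5. But Hypothesis 2a is not a cap on non-completion, and not every non-completer meets the conditions.
- **That the affected patients are frailer, or that bias has a known size or direction.** The document gives no basis for either.

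**Conclusion.** The concern holds in a limited form. The visit text and the schedule footnote set different anchors for the primary-outcome visit in the experimental arm, and the schedule and the text differ on the window. These passages must be reconciled.

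Under the visit text, a patient who stops after usual care has ended can be assessed up to 24 to 26 days before a comparable control's day 42 (stopping after visit 1), even on the last permitted day. The window also closes 10 to 12 days before the resume period ends, counted from the last attended visit.

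Under the footnote there is no early assessment. The clash with the resume period remains only for a last attended visit after about day 30 to 32, or day 23 to 25 if the 21 days run from a cancelled weekly visit. It also requires that no usual-care visit falls late enough to extend the window.

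These figures rest on weekly visits, a first visit on day 7 and no holidays. How many patients are affected cannot be computed, because the document gives no cancellation, dropout or usual-care duration figures. The point is worth correcting because the visit text makes timing of the primary outcome depend on arm, and with 24 patients per arm a few mistimed scores could matter.

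**What to change.** Amend the Schedule of Evaluations, its footnote and the Post-intervention evaluation section so that they state one rule:

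1. **Anchor, both arms:** the latest of 6 weeks from baseline, the last usual-care visit and, in the experimental arm, the end of the programme.
2. **End of programme, for assessment dating only:** the sixth study visit or, for a patient who has stopped, the earlier of the date stopping is confirmed and the date the existing 21-day period lapses.
3. **Start of the 21 days:** the sponsor should state it. The treatment rule itself stays unchanged.
4. **Window:** one definition, the same in both arms and in table and text.
5. **Follow-up:** count Day 30 and Day 90 from the same anchor in both arms.

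Item 2 is needed because applying the control-arm rule to everyone who has not yet had six visits would catch patients who are merely late starters. With a first visit on day 10 and weekly visits, visit 6 falls on day 10 + 35 = 45. If usual care is over, a day-42 anchor would call for assessment before that visit.

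The cost is one paragraph in an amendment and no extra visits. Some non-completers would be assessed up to about 3 weeks later than a completer on the same schedule. For example, a patient who stops after visit 5 on day 35 could be anchored at day 63, against day 42 for a completer, a difference of 21 days. Experimental patients whose programme ends after both day 42 and their last usual visit will still be assessed later than controls, so actual assessment dates should be recorded and reported by arm.

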3. Jebsen Hand Function Test
4. Box and Block Test
5. Timed-Up-and Go
6. Short Physical Performance Battery
7. Adverse events questionnaire

Final evaluation or three-month follow-up evaluation.

The final evaluation will occur over the phone by the research assistant or coordinator within seven days three months after the completion of the last visit of usual home health rehabilitation therapy or ADL-enhanced intervention (Day 90 post intervention). The following assessments will be administered during the final evaluation.

1. Activity Measure of Post-Acute Care Home Health Short Form
2. Adverse events questionnaire

Data analysis plan.

Preliminary analysis. We will compare participant demographics and covariates (e.g., pain levels) between the two groups. Variables with statistically significant differences will be included in the subsequent statistical models as covariates. We will graph spaghetti plots for repeated measurements and examine for outliers.

Data analysis. Since ADL and physical functioning outcomes will be collected over three time points (baseline, post-treatment, one-month follow-up), the mixed-effects linear regression modeling will be conducted to fit the data, in which a random-effects term is included to accommodate within-subject data correlation and a quadratic growth curve is included to describe the temporal trend of the response.

For **Aim 1**, which will estimate the preliminary effect of the ADL-enhanced program on improving ADL, three separate mixed-effects regression analyses will be conducted for the Motor Skills scores of the Assessment of Motor and Process Skills (the primary outcome), the Activity Measure of Post-Acute Care Home Health Short Form, and the OASIS self-care items, in each of which sex, race, age, and other covariates will be included in the model.

For **Aim 2**, which will estimate the preliminary effect of the ADL-enhanced program on physical functioning of the upper extremity and lower extremity, four similar separate analyses will be conducted for the Box and Block Test, Jebsen Hand Function Test, Timed-Up-and Go, and Short Physical Performance Battery.

For **Aim 3**, the program completion rate and satisfaction rate will be compared to the benchmark, 75%. Fisher's Exact Test will be performed to compare the proportion of patients who experience adverse events of hospitalization, emergency room visits, or falls (adverse event rate) between the two groups.

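### The sections that date the follow-up assessments contradict each other; read literally, they shorten the control arm's post-intervention to one-month interval below the experimental arm's nominal 30 days

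*Combined protocol and SAP*

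**What the plan says.** Follow-up is dated in four places.

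- **Post-intervention evaluation, experimental arm:** the visit takes place "within seven business days after the completion of the last visit of usual home health rehabilitation therapy or ADL-enhanced intervention, whichever occurs last". This sentence has no 6-week minimum.
- **Post-intervention evaluation, control arm:** the visit "will occur either 6 weeks after the baseline assessment or after the last usual home health visit, whichever occurs last". The term for the home health visit is not defined anywhere.
- **Schedule of Evaluations (6.1), footnote to the post-intervention column:** "The end of ADL-enhanced program, the last home visit of usual care, or 6 weeks from the baseline assessment, which occurs last". This rule makes no distinction between arms.
- **One-month and 3-month sections:** the first is due "one month after the completion of the last visit of usual home health rehabilitation therapy or ADL-enhanced intervention (Day 30 post intervention") and the second "three months after the completion of the last visit of usual home health rehabilitation therapy or ADL-enhanced intervention (Day 90 post intervention"). The table header for the one-month column reads "Day 30 post intervention \pm 7 Business days".

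On usual care, the Allowed interventions paragraph says "The care plan should include regular home health rehabilitation therapy". That does not confine agency care to therapy, but no other type of visit is named. The Data analysis plan fits a mixed model with a quadratic time curve to baseline, post-treatment and one-month data. It does not say whether time is entered as nominal visit or actual days.

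**The concern.** The hypotheses for ADL and for physical function each have two parts: more improvement at completion, and less decline afterwards. The second part compares change from the post-intervention visit to the follow-up visits, so those visits should be spaced alike in the two arms. Here the event that starts the follow-up clock for controls is not necessarily the event that dated their post-intervention visit. In the experimental arm the two events are the same.

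A shorter control interval leaves controls less time to decline or to go on recovering. A between-arm difference in change over that interval then partly reflects its length. The quadratic curve is affected too: if visits are coded nominally, the model treats unequal intervals as equal.

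**Working it through.** There is no stated figure to reproduce; the check is calendar arithmetic with baseline as day 0.

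**Inputs.** From the documents: the 6-week point is day 42; follow-up is at 30 and 90 days; the program is six visits over six weeks, so program end E is about day 42 if it starts at baseline; a patient has 21 days to resume after an interruption. Assumed, because the documents give no distribution: T, the last usual therapy visit, and H, the last home health visit. The illustrations keep H at or below day 60, the study period named under Adherence Assessment, although that is not stated as a limit on agency visits.

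**Formulas from the text of the visit sections.**
- Control: post-intervention = max(42, H); one-month = T + 30; gap = T + 30 − max(42, H).
- Experimental: post-intervention = max(T, E); one-month = max(T, E) + 30; gap = 30.

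| T | H | Control post-intervention day | Control one-month day | Control gap | Experimental gap |
|---|---|---|---|---|---|
| 12 | 12 | 42 | 42 | 0 | 30 |
| 14 | 14 | 42 | 44 | 2 | 30 |
| 28 | 28 | 42 | 58 | 16 | 30 |
| 42 | 42 | 42 | 72 | 30 | 30 |
| 42 | 60 | 60 | 72 | 12 | 30 |
| 28 | 56 | 56 | 58 | 2 | 30 |
| 21 | 56 | 56 | 51 | −5 | 30 |

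**Narrow reading (H = T).** If the control wording means therapy visits only, the gap is T + 30 − 42 = T − 12 for every T below 42. The control-only 6-week floor is enough to produce this.

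**Broad reading (H can exceed T).** The gap shrinks further whenever H exceeds both 42 and T. The one-month date falls on or before the post-intervention date when H − T is at least 30, or when T is 12 or less.

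**Visit windows.** Seven business days span 9 to 11 calendar days. With T = H = 28, the control post-intervention window in the table runs to at least day 42 + 9 = 51, and the one-month window opens no later than day 58 − 9 = 49. The two windows overlap.

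**3-month visit.** With T = H = 28 the control visit is due on day 28 + 90 = 118, which is 118 − 42 = 76 days after post-intervention, against 90 in the experimental arm.

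**Timing of the post-intervention visit itself.** With E = 42 and T no later than 42, a control is seen 0 days later than a matched experimental patient when H is at most 42, 14 days later at H = 56, and 18 days later at H = 60. If one full pause moves E to 42 + 21 = 63, the experimental patient is seen 3 days after a control with H = 60. The order can go either way.

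**Footnote rule.** Applied to both arms, with Day 30 counted from the date it gives, every gap is 30 days. Applied to the post-intervention visit alone, and taking its usual-care home visit to be the same event as H, it leaves the control date at max(42, H). The one-month sentence still gives T + 30, so the control gaps in the table do not change.

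**The case against.** The strongest reply is that this is loose wording and not a difference in design. The comparator is described throughout as usual rehabilitation, so the control phrase may be shorthand for the last therapy visit. The footnote already supplies one rule for both arms, and with the table's Day 30 it can be read to give 30 days for everyone. The windows allow some drift in any case, and this is a 48-patient pilot estimating preliminary effects.

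Part of this stands. A reader might infer that controls with continuing nursing visits are systematically assessed later, and that the completion contrast is biased by some fraction of a standard deviation. The documents do not support that. They never say that visits of every kind count, and they do not mention nursing. A control is later than a matched experimental patient only if H exceeds day 42, therapy end and program end together, and the resumption window can delay program end. Any figure in standard deviations would rest on assumed shares, delays and rates of change.

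The rest does not stand. The shorthand reading still gives T − 12 days for controls whose therapy ends before week 6. The footnote shows that a common rule is workable, but the visit sections say something else and nothing states which prevails. The windows surround target dates that are themselves spaced differently by arm. The model might use actual days, but the plan does not say so.

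**Conclusion.** The point holds as an internal contradiction with a definite consequence for one comparison. Under the visit sections as written, the control interval from post-intervention to one month is below 30 days for any control whose therapy ends before day 42, on either reading of the control wording. On the broad reading it is also below 30 for any control with H later than both day 42 and T. The experimental interval is a nominal 30. The less-decline comparison and the time curve are therefore distorted by arm. How many controls are affected, and by how much, depends on T and H, which the documents do not describe.

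For the contrast at completion, neither the size nor the direction of any bias can be established. The matter is worth correcting even in a pilot, because it affects a stated hypothesis and the correction is cheap.

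**What to change.** 1. Reconcile the Schedule of Evaluations footnote with the post-intervention, one-month and 3-month sections, using one anchor with identical wording for both arms. The footnote's rule would serve, provided the usual-care visit is defined once, stating whether non-therapy visits count, and applied the same way in both arms.
2. Count Day 30 and Day 90 from that same anchor. The nominal gap is then 30 days for every patient. Changing the post-intervention wording alone would not achieve this.
3. State in the Data analysis plan how time is coded. For visits already done under the present wording, fit the mixed model with actual days since baseline as a sensitivity analysis. This also covers differences in elapsed time that remain because program end enters the anchor only in the experimental arm.

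The cost is minor rewording, one scheduling instruction to the coordinator and one extra model. Some controls would be followed for longer: with T = H = 28, the one-month visit moves from day 58 to day 72.

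### Only the experimental arm's assessment clock can be moved by programme end, so patients with a delayed programme are assessed later from baseline than comparable controls, and neither the growth model nor the adverse-event comparison is set up to allow for it.

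*Combined protocol and SAP*

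**What the plan says.** The rule for the post-intervention visit is stated twice.

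- **Schedule of Evaluations (6.1), footnote:** "The end of ADL-enhanced program, the last home visit of usual care, or 6 weeks from the baseline assessment, which occurs last". No arm is named. Control patients have no programme, so only the last two events can apply to them.
- **Post-intervention evaluation:** the control visit is "either 6 weeks after the baseline assessment or after the last usual home health visit, whichever occurs last". The experimental visit "will occur within seven business days after the completion of the last visit of usual home health rehabilitation therapy or ADL-enhanced intervention, whichever occurs last". This text does not mention the six-week floor for the experimental arm.

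Description of ADL-enhanced intervention shows that programme end can move independently of usual care: "The study OT visits will occur separately from usual therapy visits". Six visits are planned over six weeks. On delays it says "If the patient cancels a study OT visit, the visit will be rescheduled" and "The patient will have a 21-day window to resume the intervention". Adherence Assessment counts sessions completed within a 60-day study period. The programme starts after baseline and randomization, with no stated lag.

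The one-month and three-month visits are counted from the last usual-care or programme visit, and the adverse-event questionnaire is given at all three post-baseline visits. The Data analysis plan specifies a mixed model with a quadratic time trend, without saying whether time is actual days or planned visit. It compares the proportions of patients with adverse events by Fisher's exact test, without defining an observation window.

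**The concern.** Visit timing is partly set, after randomization, by an event that only one arm can have. A pause adds calendar time but no extra programme visits, so the added time is not part of the treatment. Randomization does not balance it.

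Two comparisons are exposed. First, the ADL and physical-function contrasts may compare patients at different times from baseline. Background and Rationale reports that 6% of home health patients show no ADL improvement and 36% decline between admission and discharge, leaving 100 - 6 - 36 = 58% who by implication improve. ADL status therefore changes over the home health episode. Second, a comparison of proportions with an event depends on how long each arm is watched, and a Fisher test makes no allowance for that.

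**Working it through.** The plan gives no figure for this point, so there is none to reproduce. The timing rules can be compared directly.

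**Notation, in days from baseline.** U = last usual-care visit; P = last programme visit; six weeks = 42. The visit tolerance of seven business days is left out.

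**Footnote rule.** Experimental: max(42, U, P). Control: max(42, U). Difference for the same U: max(0, P - max(42, U)), which is never negative.

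| U | P | Control | Experimental | Shift |
|---|---|---|---|---|
| 42 or less | 42 or less | 42 | 42 | 0 |
| 42 or less | 49 | 42 | 49 | 7 |
| 42 or less | 63 | 42 | 63 | 21 |
| 50 | 63 | 50 | 63 | 13 |
| 60 | 63 | 60 | 63 | 3 |

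**Post-intervention evaluation text.** Experimental: max(U, P). Control: max(42, U). Late finishers shift as above. With P = 35 and U of 35 or less, the experimental visit is on day 35 against day 42, so 7 days earlier.

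**One full pause.** Six weekly visits span 5 × 7 = 35 days, and 35 + 21 = 56 days from the first programme visit. With an assumed start lag of 2 to 7 days, P = 58 to 63. With U of 42 or less the shift is 58 - 42 = 16 to 63 - 42 = 21 days (16/42 = 38% to 21/42 = 50%). If day 60 from baseline caps delivery, the maximum is 60 - 42 = 18 days (18/42 = 43%).

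**Arm average, by simulation.** Assumed, because the documents give none of these: U uniform on days 14 to 53; start lag uniform on 2 to 7 days; each of six visits delayed with probability 5% to 15%, by 7 or 14 days. The control mean is about day 43.6.

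| Scenario | Footnote rule, no cap | P capped at day 60 | Total delay capped at 21 days |
|---|---|---|---|
| 5%, 7 days | 1.2 | 1.2 | 1.2 |
| 15%, 14 days | 10.1 | 7.7 | 7.8 |

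In the low scenario 77% of patients have no shift, and under the Post-intervention evaluation text its mean shift is about -0.1 day. In the uncapped high scenario 22% of patients accumulate 28 or more days of delay, beyond a single 21-day window.

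**Adverse events, if counted from baseline.** Assume the same constant hazard in both arms and a 30-day risk of 10%. The probability of an event by day t is 1 - 0.9^(t/30). For a control at day 42 against a patient with one full pause:

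| Visit | Control | Experimental, P = 60 | Experimental, P = 63 |
|---|---|---|---|
| Post | day 42: 13.7% | day 60: 19.0% | day 63: 19.8% |
| One month | day 72: 22.3% | day 90: 27.1% | day 93: 27.9% |
| Three months | day 132: 37.1% | day 150: 41.0% | day 153: 41.6% |

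For P = 63, varying the assumed 30-day risk from 5% to 20% gives a spurious difference of about 3 to 11 points. These figures are for fully delayed patients. Putting the arm means into the same formula at 10% risk gives 14.2% at day 43.6, against 14.6% at day 44.8 (43.6 + 1.2) and 16.5% at day 51.3 (43.6 + 7.7), a difference of roughly 0.4 to 2.3 points.

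**The case against.** The strongest reply is that the visits are anchored to completion on purpose. The objectives ask for effects at treatment completion and one and three months afterwards, in a 48-patient pilot, and most patients may have no shift at all. That stands as a reason to keep the visits where they are. It does not make the windows comparable, and estimating the effect is the primary objective.

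Several stronger readings are tempting but not supported:

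- **That later assessment gives the experimental arm extra recovery and inflates the benefit.** The background figures run from admission to discharge. They say nothing about change after usual care has ended, which is when a shifted visit can fall. The primary hypothesis expects less decline at follow-up, so later assessment could equally disadvantage the experimental arm.
- **That the average shift reaches 10 days.** That needs delays beyond one 21-day window in about a fifth of patients.
- **That the experimental arm is always later.** This holds under the footnote but not for early finishers under the Post-intervention evaluation text.
- **That the adverse-event windows certainly differ at every visit.** The look-back is undefined. If each questionnaire covers the time since the previous visit, mainly the first window lengthens and the later ones are displaced.
- **That the model uses planned visits as its time axis.** The plan does not say.

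The OASIS items come from the chart at discharge or 60 days after admission, so this trigger does not affect them.

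**Conclusion.** The concern holds in limited form. Programme end is a visit trigger that only the experimental arm can have, the protocol lets it pass day 42, and the later visits carry the offset. Late finishers are shifted under either statement of the rule. The shift is about 16 to 21 days for one full pause with usual care ending by day 42 (16 to 18 under a 60-day cap from baseline), and about 1 to 8 days on average under the footnote rule with a cap. The averages rest wholly on assumed delay rates, start lags and usual-care durations.

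For ADL and physical function, neither the direction nor the size of any bias can be settled from the documents. For adverse events counted from baseline, the direction is known: longer observation of the experimental arm works against Hypothesis 2b. The plan should be changed, because the correction is cheap; the point does not invalidate the design.

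**What to change.** 1. **Time axis.** State that the growth-curve model uses actual days from baseline. Report the arm difference at the same days from baseline in both arms, alongside the planned treatment-completion contrast.
2. **Adverse events.** Compare the arms over the same fixed number of days from baseline, using event dates, and define the questionnaire's look-back. The window must lie within the follow-up that patients in both arms complete. Under the footnote rule the three-month contact is nominally no earlier than day 42 + 90 = 132, before visit tolerance.
3. **Visit timing.** Report the distribution of visit days by arm. Changes 1 and 2 reduce the imbalance but do not fully remove it: when illness itself delays the visit, timing is related to the outcome, and modelling actual days does not correct that.
4. **Reconcile the rule.** The footnote and the Post-intervention evaluation text must agree on whether the six-week floor applies to the experimental arm. The one-month and three-month sections also state no six-week floor and should match.

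The cost is small: event dates must be recorded, a few sentences are added to the analysis plan, and events after the common window drop out of that comparison. Moving the visits to common days from baseline is not recommended, because it would replace the stated treatment-completion objective. Nothing here changes how the programme or usual care is delivered.
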